2.2 Study Design Overview

This study is a phase 3, randomized, double-blind, placebo-controlled study, to be conducted at approximately 100 study sites. Approximately 230 subjects (188 AChR-Ab+ and 42 MuSK-Ab+) will be enrolled. The study includes 4 periods, a screening period, a randomized controlled period (RCP, 52 weeks for AChR-Ab+ population and 26 weeks for MuSK-Ab+ population), an optional open-label period (OLP, up to 3 years), and an optional safety follow up period (SFP, up to 2 years after the last IP dose administration).

Subjects who do not have anti-AChR or anti-MuSK antibodies are not eligible and will not be enrolled. Subjects with MGFA classification II, III, or IV disease, MG-ADL score between 6 and 10 with > 50% of this score attributed to non-ocular items or a MG-ADL score ≥ 11 , and QMG score ≥ 11 are eligible for this study. These criteria define a population of subjects with generalized MG and inadequate symptom control.

Within each population, subjects will be stratified by region first (non-Japan vs Japan). In the non-Japan population, subjects will be further stratified according to baseline disease severity ('Baseline QMG score = 11-15' vs 'Baseline QMG score ≥ 16 ') and baseline corticosteroid use ('prednisone > 5 mg/day' vs 'prednisone ≤ 5 mg/day'), and randomized 1:1 to receive either IV inebilizumab 300 mg or placebo ([Figure 1](#) and [Figure 2](#)). In the Japan population, no further stratification will be applied due to the small sample size expected, and subjects will be randomized 1:1 to receive either IV inebilizumab or placebo.

The duration of the RCP is 52 weeks for the AChR-Ab+ population ([Figure 1](#)) and 26 weeks for the MuSK-Ab+ population ([Figure 2](#)). The primary endpoint of the study is change from baseline in MG-ADL score at Week 26 in the overall study population (AChR-Ab+ and MuSK-Ab+ populations).

Subjects who enter the study on prednisone > 5 mg/day (or equivalent dose of another corticosteroid) will have their corticosteroid dose tapered per protocol, starting at Week 4 of the RCP. Steroid tapering will continue until the subject is on a dose of prednisone 5 mg/day; the dose of prednisone 5 mg/day will then be continued until the end of the RCP. Corticosteroid treatment will not be initiated if the subject is not being treated with those at the time of randomization.

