3.5 Safety Analysis

The safety endpoints will be summarized for the RCP, OLP, combined RCP and OLP, and SFP, separately, and analyzed using treatment-policy strategy.

[REDACTED]

During the RCP, the safety analysis will be based on the safety analysis set. For the treatment-policy strategy, the analyses will include all data captured after Day 1 in RCP to the last scheduled visit in the RCP regardless of the rescue therapy use. [REDACTED]

For the combined RCP and OLP, the safety analysis will be based on the any inebilizumab analysis set using treatment-policy strategy. The analyses will include all data captured after the first IP or first inebilizumab administration date to the last scheduled visit in the OLP regardless of the rescue therapy use.

For the SFP, safety analysis will be summarized using treatment-policy strategy. The summary will include all data captured between Day 1 of SFP and the last scheduled visit in the SFP regardless of the rescue therapy use.

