3.5.1.2 Analyses for Adverse Events

[figure not shown]
AEs will be coded using the most recent version of MedDRA and reported for the overall population, AChR-Ab+ population, and MuSK-ab+ population, separately. The number and percentage of subjects reporting TEAEs, TESAEs and AESIs will be summarized by SOC and PT, severity, and relationship to the IP. If a subject reports multiple occurrences of the same AE, the highest recorded severity will be taken as the severity in the summary.

An overall summary table will be produced showing the number and percentage of subjects with at least 1 TEAE in any of the following categories: TEAEs, TESAEs, Death, TEAEs leading to discontinuation of IP, Grade 3 or higher TEAEs considered related to the investigational product etc. A summary of the most common (frequency of $\geq 5\%$) TEAEs will also be presented by PT.

The TEAEs per 100 Person-years for a specific reporting period will be summarized, where $\text{TEAEs per 100 Person-years} = 100 \times \frac{\text{Total number TEAEs for a specific study period}}{\text{Total person-years for the specific study period}}$. The person-year definition is included in

A list of TEAEs, AESIs and TESAEs described in will be summarized in RCP, OLP, combined RCP and OLP and SFP as appropriate.

In addition, the overall summary of TEAEs and summary of TEAEs by SOC and PT for treatment policy will be investigated when appropriate by age, sex, region, racial/ethnic subgroups as needed for national/regional regulatory submissions, and by ADA status at any time during RCP including baseline if data allows.

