3.5.2 Clinical Laboratory Evaluation

[figure not shown]
The lab data will be summarized for RCP, OLP, combined RCP and OLP, and SFP, respectively. The analyses for the laboratory results are listed in Table 7. The toxicity will be

summarized using NCI-CTCAE version 5 for the tests with objective criteria and NCI-CTCAE version 4 was used for the tests with subjective criteria. The international system of units will be used for all the lab data.

Table 7 Laboratory Results Analysis

Laboratory dataset	Planned Analysis
Hematology and Chemistry	
 • Summary of worst post-baseline toxicity grade • Summary of at least 2-grade shift from the baseline to the worst post-baseline toxicity grade • Summary of shift from the baseline relative to the normal range • Summary of observed values, change from baseline and percent changes from baseline •
Immunoglobulins	
 • Summary of observed values and changes from the baseline

To evaluate the association between reduced Ig levels and infections/serious infections /opportunistic infections, **proportions of subjects with these AEs** will be summarized by the worst Ig Level during the combined RCP and OLP by the categories listed in [REDACTED]. **Additionally, TEAEs by SOC and PT during the combined RCP and OLP will be summarized by the categories listed in [REDACTED] as well.**

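### The Ig-infection analysis compares crude proportions by worst Ig over unequal follow-up and ignores event order, so it can show a gradient that does not exist and dilute one that does

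*SAP*

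**What the plan says.** SAP 3.5.2 states the aim: "To evaluate the association between reduced Ig levels and infections/serious infections /opportunistic infections". The measure is "proportions of subjects with these AEs", and these "will be summarized by the worst Ig Level during the combined RCP and OLP by the categories listed in" a redacted item. TEAEs by SOC and PT are tabulated by redacted categories as well.

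SAP 3.5 fixes the subjects and the window. "For the combined RCP and OLP, the safety analysis will be based on the any inebilizumab analysis set using treatment-policy strategy", and "The analyses will include all data captured after the first IP or first inebilizumab administration date to the last scheduled visit in the OLP", whether or not rescue therapy was used.

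SAP 2.2 gives the period lengths: an RCP of "52 weeks for AChR-Ab+ population and 26 weeks for MuSK-Ab+ population", then "an optional open-label period (OLP, up to 3 years". Protocol 6.1.3 bars subjects who leave the RCP early from the OLP. SAP 4.1 includes OLP safety data up to the data cut-off of the primary analysis.

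Person-year rates are planned for TEAEs by study period (SAP 3.5.1.2, Protocol 9.4.7). They are not stated for the Ig categories.

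**The concern.** Each subject is classified by an extreme value that is known only at the end of follow-up. This has two consequences.

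- **Unequal time.** A subject followed for four years has more chances of a low Ig reading, and of an infection, than one followed for six months. A crude proportion does not separate these, so a gradient can arise from follow-up length alone.
- **No event order.** An infection in month 3 counts in the low-Ig row even if the first low value came in year 3. The reverse path is also possible. Protocol 7.2.2 names infection as a trigger of worsening and allows plasma exchange (PLEX) as rescue. Protocol 2.1.4 reports that the one severe hypogammaglobulinemia case in the earlier NMOSD study followed PLEX.

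Protocol 2.1.4 lists serious infection as an important potential risk, and Protocol 8.5 makes serious and opportunistic infections AESIs. This is the only visible analysis of Ig against infection, so its reading could shape how the risk is described.

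**Working it through.** The plan states no figure for this analysis, so there is none to reproduce.

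**Inputs from the documents.** Maximum time from first inebilizumab to the last OLP visit:

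- AChR-Ab+, inebilizumab arm: 52 + 156 = 208 weeks
- MuSK-Ab+, inebilizumab arm: 26 + 156 = 182 weeks
- placebo subjects who switch at OLP entry: 156 weeks
- inebilizumab-arm subjects who do not enter the OLP: 52 or 26 weeks or less

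The arms have 94 (AChR-Ab+) and 21 (MuSK-Ab+) subjects each.

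**Assumptions, not in the documents.** Infection rate 0.05, 0.3 or 0.8 per person-year; Ig decline 0 to 0.2 log units per year (base 0.12); between-subject SD 0.25 and within-subject SD 0.12 on the log scale; start 0.55 log units above the cut-off; 0 to 20% not entering the OLP; 0 to 10% dropout per year; Ig drawn at the hematology and chemistry visits.

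**Step 1: effect of time alone.** With one constant rate for everyone, P(at least one infection) = 1 − exp(−rate × years). At 0.3 per person-year:

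- 26 weeks: 1 − exp(−0.15) = 13.9%
- 52 weeks: 1 − exp(−0.30) = 25.9%
- 156 weeks: 1 − exp(−0.90) = 59.3%
- 182 weeks: 1 − exp(−1.05) = 65.0%
- 208 weeks: 1 − exp(−1.20) = 69.9%

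**Step 2: simulation with no true association.** There were 300 repetitions per scenario, using the protocol's arms and visit weeks and base drift. Entries are the crude proportion with infection in ever-low subjects divided by that in never-low subjects.

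| Follow-up | 0.05/year | 0.3/year | 0.8/year |
|---|---|---|---|
| Equal, 156 weeks | 0.99 | 1.01 (59.8% v 59.4%) | 1.00 |
| Everyone completes the maximum | 1.08 | 1.02 (65.3% v 63.7%) | 1.01 |
| 10% no OLP, 5%/year dropout | 1.19 | 1.14 (63.2% v 55.3%) | 1.09 |
| 20% no OLP, 10%/year dropout | 1.28 | 1.27 (61.3% v 48.4%) | 1.17 |
| 10% no OLP, 5%/year dropout, staggered cut-off | 1.41 | 1.31 (43.7% v 33.3%) | 1.22 |

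With 20% non-entry and 10% dropout at 0.3 per year, mean follow-up was 169 weeks (ever low) and 127 weeks (never low). Drift 0 gave a ratio of 1.07 and drift 0.2 gave 1.47. The ratio is about 1.0 when follow-up is equal, which identifies unequal follow-up as the source.

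**Step 3: event order.** Among ever-low subjects with an infection, the first infection preceded the first low Ig in 47 to 73% at base drift, 28% at drift 0 and 67% at drift 0.2.

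**Step 4: a true rate ratio of 2 after the first low Ig (0.3 per year).**

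- Crude proportions: 1.21 at equal follow-up; 1.50 with 20% non-entry and 10% dropout, where the follow-up artefact offsets part of the dilution.
- Person-year rates by worst category: 1.45 and 1.47.
- Person-time split at the first low Ig: 2.02 and 1.98, with null-scenario medians of 0.92 to 1.01.

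Not all of the fall from 2 to 1.21 is due to event order. Proportions of a common event compress a rate ratio: over three years, [1 − exp(−1.8)] / [1 − exp(−0.9)] = 83.5% / 59.3% = 1.41. The fall from 2 to 1.45 on the rate scale is the ordering part.

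**The case against.** **Size.** If nearly everyone completes the OLP, the follow-up artefact is negligible to small (1.01 to 1.08). A second model (Ig mean 11 g/L, SD 2.5, about 10% decline per year, 0.3 infections per year) gave 1.03 with full completion. It gave 1.10 with 3% non-entry and 3% yearly dropout, and reached 1.30 only at 20% and 10%. The one retention figure in the documents is 97.0% completion of the RCP in the NMOSD study (Protocol 2.1.3.3). This objection stands: a reader might infer that the plan must produce a spurious ratio near 1.3, and the documents do not support that. However, the 97.0% covers a 28-week period in another disease, and it says nothing of OLP entry or of the staggered cut-off.

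**Status of the table.** It is a descriptive summary with no planned test or decision rule, it speaks of association and not cause, and safety is also shown by antibody population. All true. The stated aim is nevertheless to evaluate an association, and within an antibody population follow-up still differs by arm, OLP entry and cut-off.

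**Redaction.** A timing rule in the redacted item cannot be excluded. It is cited only as a list of categories.

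**ADA.** A reader might extend the point to TEAEs summarised "by ADA status at any time during RCP including baseline if data allows". That does not follow. The grouping is confined to an RCP of fixed length, includes baseline, and AEs are reported by antibody population. Counting TEAEs only after the first positive sample would itself bias the comparison. With no true association, a 52-week RCP and first positivity spread evenly over weeks 0, 4, 12, 26 and 38 (assumed), the positive to negative ratio of proportions is 0.71, 0.76 and 0.87 at 0.3, 1 and 3 events per year.

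**Conclusion.** The concern holds for the Ig-infection analysis only. As the visible text stands, the table can show a gradient with no true association. The ratio is about 1.0 with near-complete retention. At 0.3 infections per person-year and base drift it is about 1.1 to 1.3 with OLP non-entry, dropout or a staggered cut-off. Over all the assumed inputs tried, those unequal-retention scenarios span 1.07 to 1.47.

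The lack of event order does not depend on retention, and it can dilute a real effect: a true rate ratio of 2 appears as about 1.2 in crude proportions at equal follow-up, partly because proportions compress rate ratios.

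Infection rate, Ig drift and dropout are assumptions, the category limits are redacted, and the Ig sampling schedule is not visible. Nothing here bears on the primary or key secondary results.

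**What to change.** Add to SAP 3.5.2 an analysis with time-updated Ig:

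- Assign each infection, and each interval of person-time from first inebilizumab, to the category of the most recent Ig measured before it. Use baseline Ig until the first later value.
- Report infections, serious infections and opportunistic infections per 100 person-years by category, with 95% CIs.
- Keep the worst-Ig tables and label them as descriptive only.

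Person-years by worst category would not be enough: they remove the follow-up artefact but leave the ordering error (a true 2 reads as about 1.46). The simulation split person-time once, at the first low value. The most-recent-value version rests on the same principle but was not simulated separately.

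**Cost.** More programming. AE onset dates are recorded (Protocol 8.2) and person-years are already derived by period. If Ig is drawn only at scheduled visits, values may be up to about 26 weeks old late in the OLP, where Protocol Table 5 has visits at weeks 78, 104, 130 and 156. The report should state this limit.

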3.5.3 Other Safety Evaluations

3.5.3.1 Columbia Suicide Severity Rating Scale

Two versions of the Columbia Suicide Severity Rating Scale (C-SSRS) (C-SSRS Baseline/Screening version and C-SSRS since last visit version) are collected during the study. The outcomes listed in Table 9 are C-SSRS categories and have binary responses (yes/no).

Table 9 C-SSRS Categories for Reporting

Category #	Category
1	Wish to be Dead
2	Non-specific Active Suicidal Thoughts
3	Active Suicidal Ideation with Any Methods (Not Plan) without Intent to Act
4	Active Suicidal Ideation with Some Intent to Act, without Specific Plan
5	Active Suicidal Ideation with Specific Plan and Intent
6	Preparatory Acts or Behavior
7	Aborted Attempt
8	Interrupted Attempt
9	Actual Attempt (non-fatal)
10	Completed Suicide
11	Self-injurious behavior without suicidal intent (not suicide-related)

Composite endpoints, defined as in Table 10 based on the categories in Table 9, will be summarized in the overall study population, AChR-Ab+ population, and MuSK-Ab + population, respectively, for baseline, post-baseline by week 26 in RCP, post-baseline in OLP, and post-baseline in SFP. For the AChR-Ab+ population, the composite endpoints during week 26 and week 52 in RCP will also be summarized.

Table 10 Composite Endpoints Based on C-SSRS

Endpoint	Description
Suicidal ideation	A “yes” answer at any time during the given period to any 1 of the 5 suicidal ideation questions (Categories 1-5) on the C-SSRS.
Suicidal behavior	A “yes” answer at any time during the given period to any 1 of the 5 suicidal behavior questions (Categories 6-10) on the C-SSRS.
Suicidal ideation or behavior	A “yes” answer at any time during the given period to any 1 of the 10 suicidal ideation and behavior questions (Categories 1-10) on the C-SSRS.

Analysis of C-SSRS will be restricted to subjects who have at least one response at both baseline and post-baseline visits.

3.5.3.2 Vital Signs

The observed values, along with the changes from baseline, will be summarized for systolic blood pressure, diastolic blood pressure, body temperature, pulse rate, and respiratory rate. In

addition, a summary of subjects with clinically significant vital signs values (as defined below) within 24 hours after each dosing will also be provided.

- Systolic blood pressure: < 90 mmHg, > 140 mmHg, > 160 mmHg
- Diastolic blood pressure: < 50 mmHg, > 90 mmHg, > 100 mmHg
- Heart rate: < 60 beats/min, > 100 beats/min
- Respiratory rate: < 12 breaths/min, > 20 breaths/min
- Temperature: < 36°C, > 38°C
- Body weight: decrease of $\geq 7\%$ from baseline and increase of $\geq 7\%$ from baseline.

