- c. Assessment should be performed at approximately the same time of day for all visits and, if possible, completed by the same assessor. Acetylcholinesterase inhibitors (if taken) must be held for 6 hours prior to the assessments; see [Section 6.2.5.3](#) for additional information.
- d. Fasting is not required.
- e. On inebilizumab dosing days (Day 1, 15, and 183), inebilizumab PK serum samples are to be collected predose and approximately 15 minutes ( $\pm$  5 minutes) after completion of the IP infusion. On non-dosing days, only one PK serum sample is required.  
[REDACTED]
- h. Females of childbearing potential only; must be found negative before the IP is administered.
- i. On days of IP administration, all procedures and blood sampling, except for post dose PK, must be collected before IP administration.
- j. For subjects on corticosteroids. Note: corticosteroid dispensation may occur outside of the scheduled visit timepoints if required/necessary to dispense the necessary quantity to subjects as needed. For corticosteroid tapering schedule, refer to [Table 12](#).

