**Table 5 Open-label Period Procedures for AChR-Ab+ and MuSK-Ab+ Populations**

Study Period	OLP										
OLP week	0	2	13	26	39	52	65	78	104	130	156
OLP Study Day (visit window)	Day 1 a	Day 15 (±2d)	Day 92 (±7d)	Day 183 (±7d)	Day 275 (±7d)	Day 365 (±7d)	Day 456 (±7d)	Day 547 (±7d)	Day 729 (±20d)	Day 911 (±20d)	Day 1093 (±20d) or EDV k
Urine pregnancy test h	X	X		X		X		X	X	X	X
IP administration i	X	X		X		X		X	X	X	
Assessment of AEs/SAEs	X	X	X	X	X	X	X	X	X	X	X
Corticosteroid dispense j	X		X	X	X	X	X	X	X	X	

██████████; **ADA** = anti-drug antibody(ies); **AE** = adverse event; **C-SSRS** = Columbia-Suicide Severity Rating Scale; **d** = Day; **ECG** = electrocardiogram; **EDV** = Early Discontinuation Visit; **ICF** = informed consent form; ██████████; **IP** = investigational product; **MG-ADL** = Myasthenia Gravis Activities of Daily Living; **MGC** = Myasthenia Gravis Composite; **MGFA** = Myasthenia Gravis Foundation of America; **MGQOL-15r** = Myasthenia Gravis Quality of Life-15, revised ██████████ ██████████  
██████████; **OLP** = Open-label Period; **PGIC** = Patient Global Impression of Change; ██████████; **QMG** = Quantitative Myasthenia Gravis; ██████████; **SAE** = serious adverse event; **SFU** = safety follow-up.

- For subjects choosing to continue into the OLP, end of RCP visit procedures must be completed prior to starting any procedures or doses of the first day of OLP.
- This procedure does not need to be repeated on OLP Day 1 if it was completed at the final RCP visit and the OLP Day 1 visit is done within 14 days of the final RCP visit.

- c. Assessment should be performed at approximately the same time of day for all visits and, if possible, completed by the same assessor. Acetylcholinesterase inhibitors (if taken) must be held for 6 hours prior to the assessments; see [Section 6.2.5.3](#) for additional information.
  - d. Fasting is not required.
- 
- h. Females of childbearing potential only; must be found negative before the IP is administered.
  - i. On days of IP administration, all procedures and blood sampling must be collected before IP administration.
  - j. For subject on corticosteroids; corticosteroid dispensation may occur outside of the scheduled visit timepoints if required/necessary to dispense the necessary quantity to subjects as needed.

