### 7.1.2 Monitoring of Dose Administration

Vital signs (body temperature, BP, pulse rate, and respiratory rate) must be taken with the subject in a seated position as follows:

- Within 60 minutes prior to administration of the IP
- 15 ( $\pm$  5) minutes after the start of the infusion and then every 30 ( $\pm$  10) minutes until completion of infusion
- At the completion of infusion ( $\pm$  10 minutes)
- 60 ( $\pm$  10) minutes after dosing (repeated as needed until stable)

If a hypersensitivity reaction occurs during the infusion, vital signs will be taken more frequently, as warranted by the severity of the reaction.

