3.1.4 Analysis Windows

Unless otherwise specified, analysis visit windows will be used for all visit-based assessments to map longitudinal observations to scheduled visits, since not all assessments are performed on the scheduled day. The analysis visit windows will be defined by bisecting the interval between adjacent scheduled visit days unless otherwise specified. Detailed specifications will be included in the statistical programming plan (SPP) within each study period (RCP, OLP, and SFP).

Assessments will be mapped to analysis windows using study days and the following rules will be used to select the assessment to be included in analyses:

- If more than one assessment falls within a visit window, the closest non-missing assessment to the scheduled day will be used in the analysis.
- **If more than one non-missing assessment falls on the same day, the later one will be used in the analysis.**
- If two non-missing assessment actual dates are equidistant from the target day, the later visit will be used in the analysis.

However, an unscheduled visit with the assessments listed per protocol should be performed to evaluate worsening of MG symptoms if rescue therapy is being considered per protocol. If an unscheduled visit occurred on or before the rescue therapy use in a derived visit window, the observations collected during this unscheduled visit will be selected as the observation for this visit window. For example, the derived visit window for the scheduled Day 85 is from Day 72 to Day 105, assuming 3 records (Day 83, Day 95 and Day 100) collected in this derived visit window for this scheduled Day 85 visit, and the Day 95 visit is for RT evaluation (i.e., rescue therapy starts on or right after Day 95 visit), then the observation collected on Day 95 will be used for this scheduled Day 85 visit.

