3.5.3.4 Physical Examination and Weight

[figure not shown]
The clinically important abnormal findings from the physical examinations will be recorded as AEs. The observed values and the changes from baseline in the weight will be summarized.

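### The 7% body-weight criterion sits in a 24-hour post-dose summary where no weight is scheduled, so it cannot be evaluated as written

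*SAP*

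**What the plan says.** SAP 3.5.3.2 plans two outputs for vital signs: observed values with change from baseline, and "a summary of subjects with clinically significant vital signs values (as defined below) within 24 hours after each dosing will also be provided". The list defining those values has six entries: systolic pressure, diastolic pressure, heart rate, respiratory rate, temperature and, last, "Body weight: decrease of $\geq 7\%$ from baseline and increase of $\geq 7\%$ from baseline". The 24-hour limit governs the whole list.

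The only other weight analysis in the visible SAP text is in 3.5.3.4: "The observed values and the changes from baseline in the weight will be summarized". It has no time limit and no 7% category.

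On order within a dosing day, the footnote to Protocol Table 3 says: "On days of IP administration, all procedures and blood sampling, except for post dose PK, must be collected before IP administration". Table 5 says the same for the open-label period: "On days of IP administration, all procedures and blood sampling must be collected before IP administration". Protocol 6.1.2 repeats the rule for the RCP, excepting only adverse-event collection, certain post-dose blood samples and corticosteroid dispensing.

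For several values on one day, SAP 3.1.4 says: "If more than one non-missing assessment falls on the same day, the later one will be used in the analysis". The section covers all visit-based assessments unless otherwise specified and leaves detailed window specifications to the SPP, which is not among the documents. Protocol 7.1.2 requires vital signs before, during, at the end of and about 60 minutes after each infusion.

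**The concern.** A threshold count is useful only if the measurement can fall in the window that defines it. Weight is not part of infusion monitoring, and a 7% change from baseline is not something a 24-hour post-dose window is suited to detect. If no weight is taken in that window, the SAP commits to a row that cannot be filled, and the count of subjects with a marked gain or loss is reported nowhere else. That count is of interest here because subjects entering on more than 5 mg/day of prednisone have their dose tapered during the RCP.

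The secondary question is which reading represents the visit on a dosing day. If it is the last one, change from baseline at dosing visits compares a reading taken after premedication and infusion with a pre-dose baseline. At other visits there is no such contrast, so a by-visit profile would mix two conditions.

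**Working it through.** The plan gives no figure to reproduce. The check sets the weight schedule against the dosing days.

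**Weight.** Visit days come from Protocol Tables 2 to 5 and dosing days from Protocol Table 8 and Section 6.1.3. Interval = weight day − previous dose day in the same period.

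| Period | Weight days | Dosing days | Weight on a dosing day | Interval at post-baseline weights |
|---|---|---|---|---|
| RCP, AChR-Ab+ | 1, 365/EDV | 1, 15, 183 | Day 1, pre-dose | 365 − 183 = 182 days |
| RCP, MuSK-Ab+ | 1, 183/EDV | 1, 15 | Day 1, pre-dose | 183 − 15 = 168 days |
| OLP | 1, 365, 1093/EDV | 1, 15, 183, 365, 547, 729, 911 | Days 1 and 365, pre-dose | 365 − 183 = 182; 1093 − 911 = 182 days |

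- The screening weight precedes all dosing.
- If the last RCP visit and OLP Day 1 fall on the same day, the RCP procedures must be finished before the OLP dose (footnotes to Tables 3, 4 and 5).
- The special-visit table (Table 7) shows no weight row.
- Visit windows do not change the result. The shortest scheduled interval they allow is at OLP Day 1093: (1093 − 20) − (911 + 20) = 1073 − 931 = 142 days.

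Scheduled weights within 24 hours after a dose: 0. There is one rare exception. Under Protocol 6.3.2 a visit at which a subject withdraws becomes an EDV, and the EDV includes weight. If that happens on a dosing day after the infusion, a weight could fall in the window.

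**The other five rows.** Blood pressure, pulse, respiratory rate and temperature are all measured during and after each infusion (Protocol 7.1.2). Five of the six rows can be filled as intended.

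**Vital signs by visit.** On a dosing day all readings are equally close to the target day, so the same-day rule decides. Read literally, it picks a post-infusion reading. SAP 3.1.3 keeps baseline as the last value before the first dose of the period, so baselines are not affected. Exposed post-baseline visits are:

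- RCP, AChR-Ab+: Days 15 and 183, 2 of 10.
- RCP, MuSK-Ab+: Day 15, 1 of 6.
- OLP: Days 15, 183, 365, 547, 729 and 911, 6 of 10.

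The remaining 8 of 10, 5 of 6 and 4 of 10 visits are unaffected.

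**The case against.** On weight, the defence is that this is one misplaced bullet. An empty row would be noticed in programming, and SAP 3.5.3.4 still reports weight and its change from baseline. That limits the consequence but does not restore the 7% category, which no other visible text applies.

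On vital signs the defence is stronger. Vital signs are also a row in Protocol Tables 3 to 5, so the footnote that puts weight before the infusion puts the scheduled vital-sign reading there too. The infusion readings come from a separate section on dose monitoring, and the 24-hour summary gives them their own place. A programmer could reasonably treat only the scheduled reading as visit-based, and the SPP may say so. In the RCP both arms follow the same reading schedule, so between-arm comparisons at a visit keep a common timing. All of this stands and makes the second point conditional. What remains is that the SAP states the same-day rule without a visible exemption for vital signs, so the outcome depends on a document the reader cannot check.

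**Conclusion.** The weight point holds. The criterion has no scheduled data in its stated window, so one of six rows is empty apart from a rare converted EDV, and the 7% category is lost. The vital-sign point holds only on the literal text of SAP 3.1.4. It is confined to post-baseline dosing days, which are a minority of visits in the RCP and a majority in the OLP, where there is no concurrent placebo group.

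Three stronger readings are tempting, and the documents do not support them.

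- A reader might infer that both safety tables fail. They do not: five rows of the 24-hour table work, and the non-dosing visits in the by-visit table are untouched.
- A reader might infer that the weight row will print as zero in both arms and pass for evidence of no weight effect. The SAP does not say how a row without evaluable subjects is shown, and weight change is still reported in 3.5.3.4.
- A reader might infer that the pooled Week 26 vital signs would mix 188/230 = 82% post-infusion values with 42/230 = 18% others. That assumes every AChR-Ab+ subject is still in the study and dosed at Day 183. It also assumes no MuSK-Ab+ subject is infused that day, although Protocol 6.1.3 strongly recommends holding OLP Day 1 on the day of the last RCP visit. SAP 3.1 also provides separate safety summaries by antibody population, where this mixing does not arise.

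The conclusion rests on the visible text. The SPP or redacted passages could contain an exception. Only descriptive safety outputs are involved; the primary and key secondary analyses are not affected.

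**What to change.** 1. In SAP 3.5.3.2, remove body weight from the 24-hour post-dose list. Apply the 7% decrease and increase thresholds to post-baseline weights instead, for example in SAP 3.5.3.4: end of RCP or EDV, and OLP Days 365 and 1093 or EDV. Use subjects with a baseline and at least one post-baseline weight as the denominator.
2. In SAP 3.1.4, state that on dosing days the pre-infusion vital signs are the visit value, and that readings during and after the infusion feed only the 24-hour post-dose summary. If the SPP already specifies this, a cross-reference is enough.

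The cost is two short SAP edits. No data collection, visit schedule or protocol text changes.
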